01.12.2024

Comparative Evaluation of the Possible Effects of Platelet Rich Plasma (Prp) and Low Level Laser (Biolase) on Postoperative Complications and Wound Healing After Extraction of Impacted Wisdom Teeth

Study Protocol

The study was conducted on a total of 30 patients aged between 18 and 40 years who applied to the XXX Oral and Maxillofacial Surgery Department Clinic for bilateral, similar position, half mucosa and bone retention lower impacted wisdom teeth extraction. First, clinical and radiological evaluations were performed on the patients. In the clinical evaluation, systemic status, tooth deficiency, occlusion and the status of the impacted tooth were evaluated. Panoramic film was taken for radiographic evaluation.

Inclusion criteria;

- Individuals aged 18 years and over,
- Patients with partially impacted wisdom teeth,
- Individuals with systemic status according to ASA classification as ASA0 and ASA1,
- Individuals who have not used any medication in the last two weeks,
- Individuals who do not have a missing lower second molar.

Exclusion criteria for the study;

- Individuals with mouth opening less than 25 mm for various reasons,
- Pregnant and breastfeeding individuals,
- Individuals who do not come to postoperative check-ups,
- Individuals using different medications other than the recommended medication.

Individuals who were allergic to the study drugs and the materials to be used were excluded from the study. All patients were included in the study after detailed information about the study was provided and a consent form was signed by the patient. The study was initiated after permission was obtained from the XXX University Ethics Committee. (Decision No:) All operations were performed by the same physician in the operating room of the XXX University Faculty of Dentistry, Department of Oral and Maxillofacial Surgery, adhering to surgical principles and sterilization rules, under equal operating conditions.

Study groups; Randomized, prospective, split mouth and single core, 30 patients in total were divided into two groups.

Study groups were determined as follows:

- A. Platelet-rich plasma (PRP) applied group.
- B. Low-level laser therapy (LLLT) applied group.

First group (one side of the same patients): Platelet-rich plasma (PRP, initially 1200 revolutions per minute (rpm), 10 minutes later 2000 rpm for 10 minutes); second group (other side of the same patient): low-level laser treatment, diode laser (Ezlase 940; Biolase Technology, Inc., Irvine, CA) 100 mW (0.1 W) was applied for a total of 120 seconds. After the surgery, these two groups (methods) were applied to the extraction socket at different times (with a 2-week interval between each surgery). Both surgical sites were sutured with 3/0 silk suture (18 mm, 3\8 sharp, 75 cm black, Dağsan Silk Suture). It was randomly determined which material would be used first on which side. The other side was operated on after 2 weeks. Using an automatic centrifuge machine, PRP was initially prepared at 1200 rpm for 10 minutes and then 3 layers were created. 1) An upper straw-colored PPP (platelet-poor plasma). 2) A middle cloudy layer rich in platelets. 3) A lower layer rich in red blood cells. The straw-colored upper layer was collected together with the cloudy layer and centrifuged again at 2000 rpm for 10 minutes. Leukocyte-rich PRP was formed at the bottom of the test tube; the upper PPP was discarded using a pipette. 1 ml (10%) calcium chloride was added to the Platelet Rich Plasma for activation. (50 microliters of 10% calcium chloride is added for 1.0 mL of PRP). Gel was formed after 10 minutes. This layer consisting of approximately 2 ml of PRP was then placed in the extraction socket within 2 minutes after surgical removal of the mandibular third molar. The second group received a single session of intraoral 940 nm diode laser (BIOLASE) for 120 seconds immediately after suturing.

The patients were checked in the first session they came to, and on the 2nd and 7th days after the operation. After the operation in all patients; Amoxicillin 1000mg (Largopen 1000mg,2*1 (Bilim Ilac Sanayii Ve Ticaret A.S. Istanbul, Turkey), Dexketoprofen 25mg (Arveles 25mg, 2*1 (Menarini, Istanbul, Turkey)), benzylamine HCl + chlorhexidine gluconate gargle (Andorex 200ml gargle, 3*1 (Humanis Sağlık A.S. Istanbul, Turkey) were used routinely. Sutures were removed after 1 week. Pain was assessed with Visual Analog Scale (VAS) at 3, 6, 9, 12 and 24 hours and on days 2, 3, 4, 5, 6 and 7. Angulus-tragus, angulus-lateral canthus, angulus-nasalis, angulus-labial commissure and angulus-pogonion points were used to evaluate edema. Measurements were made immediately before, 2 days after and 7 days after the operation. For the evaluation of trismus, mouth opening - the distance between the incisal edges of the central teeth during maximum mouth opening - was measured immediately before, 2 days after and 7 days after the operation. As a result, statistical analysis was performed and interpreted for the

obtained data. Before surgical extraction of the impacted tooth, the inferior alveolaris and buccal nerve were local anesthetized and the buccal flap was elevated mucoperiosteally with a 'Winter' incision using a scalpel number 15. A 1.6 mm diameter steel carbide round cutter, fissure cutter burs, a surgical micromotor operating at 1400 rpm and serum irrigation were used to remove the bone. The teeth were exposed. The teeth were then divided into two by bur and extracted with the help of a dental elevator. During the operation, 2 ampoules of local anesthetic (Ultracain 69 DS forte-Aventis İlaç Sanayi Tic. A1, Turkey) containing 40 mg/ml articaine HCl and 0.012 mg/ml epinephrine HCl were used as local anesthetic solution in all groups. The flap was closed primarily with 3/0, 19 mm atraumatic silk sutures and 3/8 round needles. The time between the first incision and the last suture was calculated and recorded.

Statistical Analysis Plan

All statistical analyses were performed in a statistical software program (SPSS version 26.0, IBM Corp.). Mean, standard deviation, median, minimum and maximum values were calculated for descriptive statistics. Categorical data were shown with frequency and percentage. The conformity of the data to normal distribution was evaluated by examining the Shapiro-Wilk test and histograms. Comparisons between the two treatment groups were made with the Student-T test for data suitable for normal distribution, while the Mann-Whitney U test was used for data not suitable for normal distribution. In order to find statistical differences in the time-dependent changes in the measured data in both treatment groups, repeated measures ANOVA test was used for normally distributed data and Bonferroni test was used for post-hoc comparisons. Friedman test was applied to non-normally distributed data and Dunn-Bonferroni test was used for post-hoc comparisons. Chi-square test was applied for comparison of categorical data. Significance level was determined as $p<0.05$.

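### Missing a postoperative check-up is listed as an exclusion criterion, although it can only happen after randomisation and treatment, and the SAP defines no analysis set that keeps the patients it removes

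*Combined protocol and SAP*

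**What the plan says.** The Study Protocol has two criteria lists. Under the exclusion criteria are "Individuals who do not come to postoperative check-ups" and "Individuals using different medications other than the recommended medication". Prior medication is covered separately, under the inclusion criteria: "Individuals who have not used any medication in the last two weeks".

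On size: "The study was conducted on a total of 30 patients aged between 18 and 40 years". The design is split-mouth, with the second side operated on two weeks after the first. On allocation: "It was randomly determined which material would be used first on which side".

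On follow-up: "The patients were checked in the first session they came to, and on the 2nd and 7th days after the operation". Edema is measured before surgery and on days 2 and 7, and mouth opening likewise "was measured immediately before, 2 days after and 7 days after the operation". Pain is "assessed with Visual Analog Scale (VAS) at 3, 6, 9, 12 and 24 hours and on days 2, 3, 4, 5, 6 and 7"; the text does not say how the scores were collected between visits.

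The Statistical Analysis Plan covers software, descriptive statistics, tests and the significance level. It names no analysis set and gives no rule for missed visits, withdrawals or replacement of patients.

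**The concern.** An exclusion criterion should be decidable before randomisation. This one is not: it can act only by taking out patients who have already been randomised and treated. Because the criterion is worded for individuals and each patient carries both treatments, the natural reading is that a whole pair goes.

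Two things are at stake. The first is precision, in a study of about 30 pairs. The second is that the analysed group becomes one selected by behaviour after treatment. Someone with much pain, swelling or trismus may be less likely to return, or more likely, and experience with the first side may decide whether the second is followed up. The reader cannot tell who is in the denominator.

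**Working it through.** **No figure to reproduce.** The documents give no power, effect size, standard deviation or dropout rate. The figures below are illustrations, with assumptions marked.

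**1. Order of events.** Random allocation of material, side and order; first operation; check-ups on days 2 and 7; second operation after two weeks; check-ups on days 2 and 7. That is 2 visits × 2 sides = 4 postoperative check-ups per patient. The earliest one that can be missed is day 2 after the first operation, when one side is already treated.

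**2. Precision, if 30 were randomised.** The half-width of a 95% interval for a mean paired difference is t(0.975, n−1) × SD / √n. In units of the SD of the paired difference:

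| Pairs | t | t/√n | Relative to 30 |
|---|---|---|---|
| 30 | 2.045 | 0.373 | 1.00 |
| 27 | 2.056 | 0.396 | 1.06 |
| 24 | 2.069 | 0.422 | 1.13 |
| 21 | 2.086 | 0.455 | 1.22 |

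The difference detectable with 80% power (paired t-test, two-sided 5%, both assumed) rises over the same rows: 0.53, 0.56, 0.60 and 0.64 SD.

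**3. How many patients the rule could remove.** Let p be the chance of missing any one visit (assumed), and suppose that one miss is enough to exclude.

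- Misses independent: 1 − (1 − p)^4. For p = 2%, 5%, 10% this is 7.8%, 18.5%, 34.4%. Expected pairs left out of 30: 27.7, 24.4, 19.7.
- Misses fully clustered (a patient misses all four or none): p itself, so 2%, 5%, 10%. Expected pairs left: 30(1 − p) = 29.4, 28.5, 27.0.

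**4. How much of that is due to the rule.** If all attended visits are used instead, the complete pairs at a given visit under independence are 30(1 − p)² = 28.8, 27.1, 24.3. The rule's own cost is the gap to the independent figures in step 3: about 1.1, 2.6 and 4.6 pairs. With full clustering the gap is zero for visit-based outcomes, because the removed patients have no visit data. If two misses are needed, independence gives 1 − (1 − p)^4 − 4p(1 − p)³ = 0.2%, 1.4%, 5.2% removed, which costs almost nothing beyond the missed visits themselves.

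**5. If 30 are completers.** Steps 2 to 4 do not come out of the 30. What remains is an unknown number of randomised patients who are not reported.

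**6. The medication line.** It carries no date. A postoperative meaning fits best, because medication before surgery has its own inclusion criterion and the protocol sets a routine postoperative regimen. On that reading the line has the same defect, but the reading is an inference.

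**The case against.** **The criterion may be a screening judgement about who is likely to attend.** The wording describes people who do not come, not people unwilling to come, and no screening step is given. This reading is possible but not what the text says.

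**Perhaps nobody was removed, or 30 is the number left.** Both are open, and this part stands. A reader might infer a certain loss of power from 30 pairs. The documents do not support that, since they never say whether 30 were randomised or remained. The 13% figure is conditional.

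**The precision figures are not for the planned test.** This also stands. The SAP compares the treatments with a two-sample t-test or the Mann-Whitney test. With an assumed VAS difference of 1.0, SD 2 and within-patient correlation 0.5, paired-t power with 30 / 27 / 24 / 21 pairs is 75% / 71% / 65% / 59%, whereas simulating the planned two-sample t-test gives about 47% / 42% / 36% / 30%. Power falls as pairs are lost under either test. The gap between the two tests is a separate matter and no part of this point.

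**Missed visits cluster, and suture removal at one week gives patients a reason to return.** Fair. A reader might take 8% / 19% / 34% as expected losses, but those rates need independence and a one-miss trigger. The documents support no particular miss rate.

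**The cost may be small.** Under a two-miss rule or full clustering, it nearly vanishes for visit-based outcomes. That limits the weight of the point. It does not make a post-treatment event a valid exclusion criterion.

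**Conclusion.** The point holds in limited form. It is certain from the text that a post-treatment event sits among the exclusion criteria, with no stated trigger, no statement of whether one side or both are dropped, and no analysis set in the SAP. Whether it changed the results is unknown; the number removed could be zero.

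If 30 were randomised, the precision cost runs from nothing to an interval about 13% wider with 6 pairs lost and 22% wider with 9. If 30 are completers, the issue is unreported selection instead.

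A reader might infer that the comparison is biased in a known direction, for instance towards no difference. The documents do not support that. Attendance could depend on pain, swelling, trismus or the first-treated side, so selection bias is possible, but neither its direction nor its size can be derived. Nor can bias be confined to the medication line, since attendance itself may be related to outcome.

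Overall this is a cheap improvement that should be made, of minor to moderate size.

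**What to change.** - Limit the exclusion criteria to facts known before surgery. Move non-attendance, and other medication if postoperative use is meant, to a section on deviations and withdrawals.
- State that the main analysis includes every randomised patient with any postoperative data, by the treatment randomised to each side, using all attended visits in a within-patient (paired or mixed-model) analysis.
- State whether 30 is the number randomised or the number analysed, and whether anyone was replaced.
- Report the number, timing and reason of missed visits and of other-medication use, by treatment and side.
- Keep the compliant-only set as a sensitivity analysis. Define how many misses trigger removal and whether one side or both are dropped.

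The cost is wording, one count table and a little extra analysis. The protocol is written in the past tense; if visits are complete, the set and counts can still be stated provided removed patients' data were kept. If nobody was removed, one sentence saying so settles the matter.

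Limits: edema and mouth opening missed on day 2 or 7 stay missing whichever set is used. VAS may be missing too, depending on how it was collected, and VAS recorded after other medication partly reflects that medication. The gain is a defined randomised set and retained data, not a guarantee against bias.

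### Of the three outcomes with a described measurement, only pain has no preoperative value; this does not bias PRP versus laser in expectation, but a cheap reference and check is lost

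*Combined protocol and SAP*

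**What the plan says.** The Study Protocol's paragraph on follow-up assessments sets the pain ratings as follows: "Pain was assessed with Visual Analog Scale (VAS) at 3, 6, 9, 12 and 24 hours and on days 2, 3, 4, 5, 6 and" (ending on day 7). No other part of the document supplies an earlier VAS, and the text does not say which side the patient is to rate.

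The same paragraph treats the other two measured outcomes differently. For edema: "Measurements were made immediately before, 2 days after and 7 days after the operation". Mouth opening "was measured immediately before, 2 days after and 7 days after the operation".

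The design is given under Study groups as "Randomized, prospective, split mouth and single core, 30 patients in total were divided into two groups", and the paragraph on treatments adds: "It was randomly determined which material would be used first on which side". The two operations are 2 weeks apart.

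The Statistical Analysis Plan compares treatments with a Student t or Mann-Whitney U test. It then applies repeated measures ANOVA or Friedman, with post-hoc comparisons, "In order to find statistical differences in the time-dependent changes in the measured data in both treatment groups". It names no baseline covariate, no change score and no period or order term.

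**The concern.** Two of the three measured outcomes have a preoperative value. The one rated most often does not. Patients come for removal of partially impacted teeth, so some may already have pain on one or both sides. The second operation comes 14 days after the first, but first-side ratings stop at day 7, so 14 − 7 = 7 days go unrecorded and nothing shows whether first-side pain has gone.

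Three things are at stake:

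- **The time course.** It can describe pain from 3 hours onward, but cannot relate it to the state before surgery.
- **The absolute VAS level within each treatment.** It may contain pain that does not come from the operation being assessed.
- **Chance differences.** With 30 patients, PRP and laser sides may differ in starting pain, and there is no means of seeing or adjusting for this.

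**Working it through.** The plan gives no sample size, power or effect-size figure, so there is nothing to reproduce. The check has four steps.

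**1. Count of time points (Study Protocol, follow-up assessments).**
- Pain: 5 (hours) + 6 (days 2 to 7) = 11, of which 0 are preoperative.
- Edema: 3, of which 1 is preoperative. Mouth opening: 3, of which 1 is preoperative.
- If the post-hoc step takes all pairs, pain has 11 × 10 / 2 = 55 contrasts and none involves the state before surgery. Edema and mouth opening have 3 × 2 / 2 = 3 each, and 2 of the 3 do.

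**2. Effect of leftover pain on PRP minus laser.** Input from the documents: n = 30 patients, each receiving both treatments, order random. Assumptions: simple 1:1 randomisation of order (the method is not described) and c VAS units of leftover pain at every second operation, whichever treatment came first. Let K be the number of patients given PRP second, K ~ Binomial(30, 0.5). Then

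shift in mean paired difference = c(2K − 30)/30, with expectation 0 and SD = c/√30 = 0.183c.

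| c (assumed, VAS units) | Expected shift | SD | 95% range |
|---|---|---|---|
| 0.5 | 0 | 0.09 | about ±0.17 |
| 1 | 0 | 0.18 | about ±0.33 |
| 2 | 0 | 0.37 | about ±0.67 |

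A simulation of 100,000 trials agrees with the formula. An exact 15:15 split gives a shift of 0. A 20:10 split gives c × 10/30 = 0.33c, and a split at least that uneven has probability 9.9%. This is chance error, not bias. Leftover pain that is the same in every patient would be removed by a period term alone. A preoperative rating helps with the part that varies between patients and sides.

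**3. Precision from using the score as a covariate.** Let r be the correlation between the within-patient preoperative difference and the postoperative difference. The documents give no value, so r = 0.2 to 0.4 is assumed. The variance factor is 1 − r²:
- r = 0.2: 0.96 (4% reduction)
- r = 0.3: 0.91 (9%)
- r = 0.4: 0.84 (16%)

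On the standard error scale this is √0.96 = 0.98 to √0.84 = 0.92.

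**4. The same score used as a change score.** If the preoperative and postoperative differences have equal variance (assumed), the factor is 2(1 − r):
- r = 0.2: 1.6
- r = 0.3: 1.4
- r = 0.4: 1.2

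Across this range subtraction loses precision while adjustment gains it. With unequal variances the factor is 1 + k² − 2rk, where k is the ratio of preoperative to postoperative SD. Its minimum over k is 1 − r², so subtraction never beats the covariate, apart from the one degree of freedom the covariate uses.

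**The case against.** The strongest reply is that little follows from the omission. VAS has a natural zero, whereas facial distances and mouth opening differ between people and mean nothing as swelling or restriction without a preoperative value. The difference in schedule is therefore not an internal contradiction. Entry requires no medication in the previous two weeks and bilateral teeth in similar position, which makes marked or one-sided pain at the first operation less likely. First-side ratings to day 7 would show whether pain was settling. All of this stands, and it lowers the severity. It does not remove the point: the medication criterion does not exclude pain and says little about the second operation, since every patient receives an analgesic after the first.

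A reader might go further than the documents allow in three ways:

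- **That earlier or leftover pain confounds PRP with laser.** It does not in expectation, because each patient receives both treatments with order and side random.
- **That a treatment effect already present at 3 hours would be subtracted out of later changes.** The Statistical Analysis Plan defines no change score and names no baseline. Neither the between-treatment test nor the test over time requires subtracting the 3-hour value.
- **That pain is the only outcome without a preoperative value.** This holds among the three outcomes with a described measurement. The title also names wound healing ("Postoperative Complications and Wound Healing After Extraction of Impacted Wisdom Teeth"), for which no measure or time point is given.

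**Conclusion.** The point holds as a minor one. No VAS is taken before treatment, so the planned pain time course has no preoperative reference, absolute levels cannot be cleared of pre-existing or first-side pain, and chance imbalance among 30 patients can be neither checked nor adjusted for. The PRP-laser comparison is not biased in expectation.

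That last statement assumes that randomisation was carried out as described and that any leftover pain does not depend on which treatment came first. The documents give no sign that it does, and a first-side rating before the second operation would allow a check. Pain before either operation is a possibility, not something the documents show. The precision gain of 4% to 16% in variance rests on the assumed r of 0.2 to 0.4 and will be at the low end or below if most preoperative scores are near zero.

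**What to change.** - **Collect.** Add one VAS mark just before each operation for the side about to be operated on, in the session where edema and mouth opening are already measured. Before the second operation, add a mark for the first side. State on the form which side is being rated.
- **Analyse.** Make the preoperative score the first point of the pain time course. Compare PRP with laser within patients, with the preoperative score as a covariate and a term for period. Do not use a change score, and do not label the 3-hour value a baseline. Use the first-side mark as a check on leftover pain rather than as a covariate, because it is taken after the first treatment and could be affected by it.
- **If data are already collected.** The document is written in the past tense. The period term can still be added, and the missing preoperative score stated as a limitation on reading the time course and the absolute levels.

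Cost: one mark at the first operation and two at the second, so 3 × 30 = 90 marks in all, with no extra visit. If all pairs of times are compared, the post-hoc set grows from 55 to 12 × 11 / 2 = 66, and the Bonferroni threshold falls from 0.05/55 = 0.00091 to 0.05/66 = 0.00076. Pre-specifying only the contrasts of interest avoids that.

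### The plan does not say how five facial distances form the edema outcome or which visit is primary, which leaves room for ten unadjusted PRP-versus-laser tests of one construct

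*Combined protocol and SAP*

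**What the plan says.** The Study Protocol lists the edema measurements in one sentence, "Angulus-tragus, angulus-lateral canthus, angulus-nasalis, angulus-labial commissure and angulus-pogonion points were used to evaluate edema", and gives their timing in the next: "Measurements were made immediately before, 2 days after and 7 days after the operation". It mentions no sum, mean, percentage change or other swelling score, and names no leading distance or visit. It also does not say that each distance is to be tested separately.

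The design is within-patient. The protocol describes it as "Randomized, prospective, split mouth and single core, 30 patients in total were divided into two groups", with one side given PRP and the "second group (other side of the same patient): low-level laser treatment".

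The Statistical Analysis Plan names no outcome. Its treatment comparison is generic: "Comparisons between the two treatment groups were made with the Student-T test for data suitable for normal distribution", with Mann-Whitney U otherwise, at a 0.05 level. Bonferroni-type correction appears twice, each time attached to change over time: "repeated measures ANOVA test was used for normally distributed data and Bonferroni test was used for post-hoc comparisons" and "Friedman test was applied to non-normally distributed data and Dunn-Bonferroni test was used for post-hoc comparisons". Neither covers the comparison of treatments across several distances or visits.

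**The concern.** Swelling is one construct, but it is recorded as five distances that share the angulus as a landmark, each at two postoperative visits. With no rule for combining or ranking them, two problems follow.

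- One significant distance at one visit could be reported as an edema effect when it arose by chance.
- The results may point different ways, and the plan does not say which of them answers whether swelling is less with PRP or with laser.

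An open choice can also be settled after the results are known. If a combined score was intended, its formula is still missing, so the gap exists on either reading.

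**Working it through.** The plan gives no power, SD, correlation or family-wise error figure, so there is nothing of its own to reproduce.

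**Inputs from the documents.** Five distances; two postoperative visits (days 2 and 7); 30 patients, each contributing both treatments; 0.05 per test (taken as two-sided, since the plan does not say).

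**Inputs assumed.** Correlation r between distances, 0.3 to 0.8 (0.9 as an extreme); correlation 0.5 between days 2 and 7; within-patient correlation w between the two sides, 0 to 0.7; equal SDs across distances.

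**1. Number of tests.** 5 distances × 2 visits = 10. Other readings of the silence give 2 (one score, both visits), 5 (one visit) or 15 (baseline compared as well).

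**2. Chance of at least one false positive, independent tests.** 1 − 0.95^10 = 0.401, with 10 × 0.05 = 0.5 false positives expected.

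**3. The same chance with correlated distances.** Simulation of ten t tests, 30 patients, 20,000 replicates:

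| Test | r = 0.3 | r = 0.5 | r = 0.7 | r = 0.8 |
|---|---|---|---|---|
| Paired | 36% | 32% | 26% | 22% |
| Independent-samples, w = 0 | 36% | 31% | 26% | 22% |
| Independent-samples, w = 0.3 | 16% | 15% | 12% | 11% |
| Independent-samples, w = 0.5 | 6.0% | 5.4% | 4.6% | 3.8% |
| Independent-samples, w = 0.7 | <1% | <1% | <1% | <1% |

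At r = 0.9 with a between-visit correlation of 0.8, the paired figure is about 16%.

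The lower rows fall because an independent-samples test overstates the standard error of a within-patient difference by 1/√(1 − w): 1.20, 1.41 and 1.83 at w = 0.3, 0.5 and 0.7. The same overstatement costs power.

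**4. Disagreement between lines.** With a true paired difference of 0.4 SD on every line at one visit, some but not all five paired tests are significant in 79%, 67%, 52% and 43% of simulated trials (r = 0.3, 0.5, 0.7, 0.8). Mixed results would be common even under a uniform effect.

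**5. Precision of a combined score.** The SD of the five-line mean relative to one line is √((1 + 4r)/5): 0.66, 0.77, 0.87 and 0.92 at the same r, and 0.96 at r = 0.9. A sum gives the same test as a mean. For a 0.4-SD paired difference on every line and 30 pairs, power is 56% for one line and 89%, 78%, 68% and 64% for the score.

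**6. After combining.** One score at two visits leaves a family-wise error of 1 − 0.95² = 9.75% if independent (about 8–9% simulated). One primary visit gives 5%.

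**The case against.** The strongest reply is that the plan never says it will run ten tests. A reader might infer that the distances are deliberately kept apart and never combined. The documents do not support that, because the protocol's sentence fits a sum or a mean as well as five separate analyses. Ten is likewise one count among several. This stands: what can be shown is an undefined endpoint, not a planned set of ten tests.

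A second reply concerns the error rate. A reader might take 22–40% as the rate of the plan as written. By pairing Student's t with Mann-Whitney U, the Statistical Analysis Plan appears to intend independent-samples tests. If the two sides of a patient are positively correlated, such tests are conservative here, and the rate could be near or below 5%. This also stands, but it does not rescue the plan. The protection comes from ignoring the split-mouth pairing, and once a paired test is used the higher figures apply.

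A third reply is that comparing the score with a single line flatters the score. Under the same assumptions (paired tests, 0.4 SD on every line), at least one of ten tests is significant in about 98%, 96%, 92% and 89% of trials at r = 0.3, 0.5, 0.7 and 0.8. That sensitivity is bought with the inflated error, but it does show that the plan does not rest on the 56% of one line. The gain from combining also needs equal SDs and a uniform effect, and the documents give no data on either. A raw sum gives most weight to the most variable lines.

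**Conclusion.** The concern holds as a gap in definition. The plan does not state how five distances become the edema outcome or which postoperative visit is primary, and it has no multiplicity control for PRP versus laser.

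If every distance is tested at both postoperative visits with paired tests, the chance of a false edema finding is at most about 40%. It is about 22–36% for between-distance correlations of 0.8 down to 0.3, with a day 2 to day 7 correlation of 0.5. These correlations are assumptions. With independent-samples tests the figure depends on the within-patient correlation and may be small.

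It would be too strong to say that the plan gives up a known amount of precision. The reduction in SD runs from about 34% at r = 0.3 to about 4% at r = 0.9, and the documents do not show where in that range the trial lies. The main reason to define one score is to have a single, interpretable answer with controlled error; any gain in precision is secondary. The change should be made, since edema is one of the three clinical outcomes described, alongside pain and trismus.

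**What to change.** Add to the Statistical Analysis Plan:

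1. For each operated side and visit, the edema outcome is the sum of the five distances.
2. The analysis variable is the change from that operation's own preoperative score, compared as the PRP-minus-laser difference within patient by a paired method.
3. One of the two postoperative visits is named primary for edema, and the other is secondary. Without this step, two unadjusted tests remain.
4. The five single distances are tabulated by treatment and visit, without p-values.

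The protocol is written in the past tense. If results by treatment have already been seen, the report should say that the score and the primary visit were chosen afterwards.

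The cost is wording only, because every measurement needed is already listed. The downside is that an effect confined to one line is diluted in the sum, though it stays visible in the descriptive table.
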